### 6.1.2.2 Continuous Variables

Continuous efficacy variables are:

- Raw value and change from baseline in the following assessments:
  - TJC (68 joints)
  - SJC (66 joints)
  - CRP
  - ESR
  - SGAP (VAS) (100 mm VAS)
  - SGA (VAS) (100 mm VAS)
  - PGA (VAS) (100 mm VAS)
  - HAQ-DI (See Section 10.5 Appendix 5: Computation of HAQ-DI Score)
  - DAS28-CRP score
  - DAS28-ESR score
  - SF-36v2®

- SDAI score
- CDAI score
- WPAI score
- mTSS
- Joint Space Narrowing Score
- Erosion Score
- Yearly progression of mTSS

Note: yearly progression will be calculated as follows.

[the final value of mTSS up to Week 52] - [the baseline value of mTSS]

-----x 365.25  
[date of the final value of mTSS up to Week 52] - [date of baseline value of mTSS]

Note: if subject switched from placebo then the final value of that subject is the final value before switching placebo.

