  - The mean-standard deviation plot of actual values and changes from baseline will be presented for DAS28-CRP and DAS28-ESR.

<mTSS, Erosion Score, and Joint Space Narrowing Score>

In this analysis, mTSS, Erosion Score, and Joint Space Narrowing Score will be imputed using linear extrapolations as described in the primary analysis.

- Categorical variables at each visit (including Week 28/ET, Week 52/ET) will be analyzed using Fisher's exact test.
  - mTSS change from baseline  $\geq 3$
  - mTSS change from baseline  $\leq 0.5$
  - mTSS change from baseline  $\leq 0$
- Yearly progression of mTSS will be analyzed
- Percentage of subjects showing Rapid Radiographic Progression: RRP (Yearly progression of mTSS  $\geq 5$ )
- Raw value and change from baseline variables at each visit (including Week 28/ET, EOT) will be analyzed using the RANCOVA model with treatment group (Placebo, ASP015K 100 mg, ASP015K 150 mg) as factor and baseline rank mTSS as covariate.
  - mTSS (Week 52/ET)
  - Erosion Score (Week 28/ET, Week 52/ET)
  - Joint Space Narrowing Score (Week 28/ET, Week 52/ET)
- Graphical analysis (including Week 28/ET, Week 52/ET).
  - Cumulative probability plot for the change from baseline in mTSS score, Erosion Score, Joint Space Narrowing Score will be presented at Week 28/ET, Week 52/ET.
  - Scatter plot for mTSS score at baseline to mTSS at Week 28/ET, Week 52/ET will be presented.
  - Scatter plot for mTSS score at baseline to mTSS change from baseline at Week 28/ET, Week 52/ET will be presented.

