### **Missing Data in mTSS**

For mTSS, Erosion Score, Joint Space Narrowing Score, will be imputed by linear extrapolation at Week 28 evaluation (Day197) described as Week 28/ET. Namely, for subjects who discontinued at or before Week 28 (after Day48) or for initially placebo treated subjects who switched to receive ASP015K at Week 12 due to the lack of efficacy, mTSS at Week 28 (Day 197) will be extrapolated using linear extrapolation method based on the mTSS at baseline and early termination (after Day48) or Week 12 (Day85) (before switching). For subjects who initially treated placebo, if the subjects have the measurement data at Week 28 (from Day 160 to Day 234) and not switched to ASP015K yet, then that data will be used (No imputation will be done). For Week 52 (Day365) evaluation, described as Week 52/ET, the value will be extrapolated as well (at baseline and early termination (after Day48) or Week 12/Week 28 (before switching for placebo treated subjects). If the subjects have the measurement data at Week 52 (from Day 328 to Day 402) and not initially randomized to placebo, then that data will be used (No imputation will be done).

For use in sensitivity analysis, mTSS, Erosion Score, Joint Space Narrowing Score will be imputed using LOCF. Moreover, Observed analysis will also be conducted.

In addition, Multiple Imputation for sensitivity analysis will be conducted in the following procedure.

- 1) mTSS at Week 28 will be imputed based on the regression model treatment group as factor and all mTSS values up to Week 28 as covariate. For subjects who discontinued at or before Week 28 or switched to receive ASP015K instead of placebo at Week 12 due to the lack of efficacy, mTSS data will be applied before switching. In this method, using seed as 12345, 1000 Imputed datasets will be created based on SAS ver. 9.4 PROC MI procedure, monotone regression statement.
- 2) For 1000 Imputed datasets created at Step1, Analysis of Covariance (ANCOVA) with treatment group (Placebo, ASP015K 100 mg, ASP015K 150 mg) and as factor and baseline mTSS as covariate will be conducted by each Imputed datasets and the lsmeans difference between ASP015K each group and placebo will be put.
- 3) In accordance with Rubin's rule (Little and Rubin, 2002), the 1000 estimated difference value and standard error are combined, and 95% confidence interval will be calculated. Moreover, statistical test will be conducted.

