#### **7.11.4 Handling of Schedule of Assessments of Efficacy Variables**

For data after the end of study treatment, data obtained within +2 days after the last dose is taken will be included in analysis. Baseline for efficacy is defined as value at Day 1 before the first dose of study drug for all subjects including placebo assigned subjects. For Week

12/ET, or Week 28/ET, the values at closest date to reference date will be used. As for the subjects who switched to receive ASP015K instead of placebo at Week 12, the last observation before first dose of ASP015K at Week 12 will be used for the analysis for visit Week 4, 8, 12, 12/ET. In addition, the subjects who switched to receive ASP015K instead of placebo at Week 28, the last observation before the first dose of ASP015K at Week 28 will be used for the analysis for visit Week 4, 8, 12, 12/ET, 28/ET. For EOT, the closest value to the reference date will be used regardless of the switching from placebo.

(1) TJC (68 joints)/SJC (66 joints), laboratory test (CRP)

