5.1	Percentage of subjects achieving "Good Response" or "Moderate Response" using DAS28 EULAR response criterion at each visit (Baseline, Week 4, 8, 12, 12/ET,28/ET)	X	X		Placebo, 100mg, 150mg	Fisher's exact test.
5.2	Percentage of subjects achieving "Good Response" or "Moderate Response" using DAS28 EULAR response criterion at each visit (Baseline, Weeks 4, 8, 12, 16, 20, 24, 28, 32, 36, 40, 44, 48, 52, EOT)	X	X		100mg, 150mg	No statistical test.
6.1	Percentage of subjects in ACR/EULAR remission at each visit (Baseline, Week 4, 8, 12, 12/ET,28/ET)	X			Placebo, 100mg, 150mg	Fisher's exact test.
6.2	Percentage of subjects in ACR/EULAR remission at each visit (Baseline, Weeks 4, 8, 12, 16, 20, 24, 28, 32, 36, 40, 44, 48, 52, EOT)	X			100mg, 150mg	No statistical test.
7.1	Percentage of subjects in SDAI <= 3.3 at each visit (Baseline, Week 4, 8, 12, 12/ET,28/ET)	X			Placebo, 100mg, 150mg	Fisher's exact test.
7.2	Percentage of subjects in SDAI <= 3.3 at each visit (Baseline, Weeks 4, 8, 12, 16, 20, 24, 28, 32, 36, 40, 44, 48, 52, EOT)	X			100mg, 150mg	No statistical test.

8.1	Percentage of subjects in CDAI $\leq$ 2.8 at each visit (Baseline, Week 4, 8, 12, 12/ET,28/ET)	X			Placebo, 100mg, 150mg	Fisher's exact test.
8.2	Percentage of subjects in CDAI $\leq$ 2.8 at each visit (Baseline, Weeks 4, 8, 12, 16, 20, 24, 28, 32, 36, 40, 44, 48, 52, EOT)	X			100mg, 150mg	No statistical test.
9.1	Percentage of subjects achieving HAQ-DI ( $\leq$ 0.5) at each visit (Baseline, Week 4, 8, 12, 12/ET,28/ET)			X	Placebo, 100mg, 150mg	Fisher's exact test.
9.2	Percentage of subjects achieving HAQ-DI ( $\leq$ 0.5) at each visit (Baseline, Weeks 4, 8, 12, 16, 20, 24, 28, 32, 36, 40, 44, 48, 52, EOT)			X	100mg, 150mg	No statistical test.
9.3	Percentage of subjects achieving decrease of baseline HAQ-DI of at least 0.22 at each visit (Baseline, Week 4, 8, 12, 12/ET,28/ET)			X	Placebo, 100mg, 150mg	Fisher's exact test.
9.4	Percentage of subjects achieving decrease of baseline HAQ-DI of at least 0.22 at each visit (Baseline, Weeks 4, 8, 12, 16, 20, 24, 28, 32, 36, 40, 44, 48, 52, EOT)			X	100mg, 150mg	No statistical test.
10.1	Percentage of subjects showing no progression of joint damage (mTSS change from baseline $\leq$ 0.5) at each visit (Baseline, Week 28/ET, EOT)			X	Placebo, 100mg, 150mg	Fisher's exact test.

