10.2	Percentage of subjects showing no progression of joint damage (mTSS change from baseline $\leq$ 0) at each visit (Baseline, Week 28/ET, EOT)			X	Placebo, 100mg, 150mg	Fisher's exact test.
10.3	Percentage of subjects showing Clinically Relevant Radiographic Progression: CRRP (mTSS change from baseline $\geq$ 3) at each analysis visit			X	Placebo, 100mg, 150mg	Fisher's exact test.
10.4	Percentage of subjects showing Rapid Radiographic Progression: RRP (Yearly progression of mTSS $\geq$ 5)			X	Placebo, 100mg, 150mg	Fisher's exact test.

11.1	Percentage of subjects achieving SF-36v2 of difference $\geq 5$ at each visit (Weeks 4, 8, 12, 12/ET, 28/ET)	X			Placebo, 100mg, 150mg	Fisher's exact test.
11.2	Percentage of subjects achieving SF-36v2 of difference $\geq 5$ at each visit (Weeks 4, 8, 12, 28, 52, EOT)	X			100mg, 150mg	No statistical test.
Continuous Variables						
12.1.1	Raw value and change from baseline in mTSS score at each visit (Baseline, Week 52/ET)			X	Placebo, 100mg, 150mg	Descriptive Statistics RANCOVA  analysis with Week 52/ET. No multiplicity adjustment.
12.1.2	Raw value and change from baseline in Erosion Score at each visit (Baseline, Week 28/ET, Week 52/ET)			X	Placebo, 100mg, 150mg	Descriptive Statistics; RANCOVA  analysis with each visit. No multiplicity adjustment.
12.1.3	Raw value and change from baseline in Joint Space Narrowing Score at each visit (Baseline, Week 28/ET, Week 52/ET)			X	Placebo, 100mg, 150mg	Descriptive Statistics; RANCOVA  analysis with each visit. No multiplicity adjustment.
12.2.1	Cumulative probability plot for the change from baseline in mTSS score at Week 52/ET			X	Placebo, 100mg, 150mg	
12.2.2	Cumulative probability plot for the change from baseline in Erosion Score at Week 28/ET, Week 52/ET			X	Placebo, 100mg, 150mg	
12.2.3	Cumulative probability plot for the change from baseline in Joint Space Narrowing Score at Week 28/ET, Week 52/ET			X	Placebo, 100mg, 150mg	
12.3.1	Scatter plot for mTSS score at baseline to Week 28/ET, Week 52/ET			X	Placebo, 100mg, 150mg	
12.3.2	Scatter plot for mTSS score at baseline to mTSS change from baseline at Week 28/ET, Week 52/ET			X	Placebo, 100mg, 150mg	
12.4.1	Yearly Progression of mTSS			X	Placebo, 100mg, 150mg	Descriptive Statistics;
13.1.1	Raw value and change from baseline in DAS28	X	X		Placebo, 100mg, 150mg	Descriptive Statistics;

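### Rapid radiographic progression is Fisher-tested on film intervals of about 12 or 28 weeks in switched placebo subjects and about 52 weeks in ASP015K completers, so reading error alone can separate the arms

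*SAP*

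**What the plan says.** SAP 6.1.2.2 defines yearly progression as final minus baseline mTSS, divided by the days between the two films, times 365.25. For anyone who leaves placebo, "if subject switched from placebo then the final value of that subject is the final value before switching placebo". SAP 3.2 moves every placebo subject still on treatment to ASP015K at Week 12 or Week 28. The last pre-switch film is therefore taken at about one of those visits, while an ASP015K completer has a Week 52 film.

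SAP 6.1.2.1 sets rapid progression (RRP) at 5 or more per year. Appendix 2 row 10.4, "Percentage of subjects showing Rapid Radiographic Progression: RRP", assigns Fisher's exact test for Placebo, 100 mg and 150 mg. SAP 7.4.2 lists RRP but names no test for it.

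For the other mTSS cut-offs (at least 3, at most 0.5, at most 0), SAP 7.4.2 says "Categorical variables at each visit (including Week 28/ET, Week 52/ET) will be analyzed using" Fisher's exact test. Row 10.3, "Percentage of subjects showing Clinically Relevant Radiographic Progression: CRRP", agrees for the cut at 3. Under Missing Data in mTSS (SAP 7.11.1), the Week 52 rule is that "the value will be extrapolated as well (at baseline and early termination (after Day48) or Week 12/Week 28 (before switching for placebo treated subjects". An observed Week 52 film is used only if the subject has one "and not initially randomized to placebo, then that data will be used (No imputation will be done".

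Rows 10.1 and 10.2, "Percentage of subjects showing no progression of joint damage (mTSS change from baseline" at most 0.5 or at most 0, name the late visit EOT instead. SAP 7.11.4 states: "For EOT, the closest value to the reference date will be used regardless of the switching from placebo".

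**The concern.** A fixed annual cut-off applied over different intervals is a different raw cut-off in each arm. Reading error in a change score is likely to be much the same size whether the films are 12 or 52 weeks apart. Dividing by a shorter interval magnifies it, so error carries more placebo than ASP015K subjects over the line when most true rates lie below 5 per year. Linear extrapolation to Day 365 keeps the slope, so it magnifies error in the same way for change of 3 or more at Week 52/ET.

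What is at stake is a p-value on structural damage that could be read as a drug effect when the rates would have differed without one. The mTSS sensitivity analyses in SAP 7.4.1.2 all concern change at Week 28/ET, so none would expose this.

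**Working it through.** **Plan's own figure.** The documents give no rate, power or reading-error SD for RRP. The planning figures they do give (SAP 4: mean change 2.0 on placebo and 0.5 on 150 mg at Week 28, SD 4.0) reproduce the stated sample size: a t-test for a difference of 1.5 with SD 4.0 at 90% power needs 150.4, so 151 per group. I use the placebo mean and SD below.

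**Raw cut-offs** at 84, 196 and 364 days:
- RRP, 5 × days / 365.25: 1.15, 2.68 and 4.98 points.
- Change of at least 3 at Day 365, 3 × days / 364: 0.69, 1.62 and 3.0 points.

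**Model with no drug effect.** Observed change = slope × time + normal error, with the same slope distribution in every arm and slope independent of switching. Total SD at Week 28 is 4.0, so the slope part has SD √(16 − error SD²), for example √(16 − 1) = 3.873. Slopes are normal, or right-skewed gamma with the same mean and SD (for error SD 1.0, shape 0.267 and scale 7.5).

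Placebo rate = 0.5 × Week 12 rate + 0.5 × Week 28 rate; active rate = Week 52 rate. A false benefit is two-sided Fisher p < 0.05 with placebo worse, by exact binomial enumeration at 170 per arm. The nominal rate in that direction is about 2.5%.

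*RRP, near-continuous scores*

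| Slopes | Error SD | Wk 12 | Wk 28 | Wk 52 | Placebo vs active | False benefit |
|---|---|---|---|---|---|---|
| Normal | 0.5 | 0.434 | 0.432 | 0.432 | 43.3% vs 43.2% | 2.2% |
| Normal | 1.0 | 0.440 | 0.432 | 0.431 | 43.6% vs 43.1% | 2.6% |
| Skewed | 0.5 | 0.237 | 0.216 | 0.214 | 22.7% vs 21.4% | 3.6% |
| Skewed | 0.75 | 0.281 | 0.222 | 0.216 | 25.1% vs 21.6% | 9.4% |
| Skewed | 1.0 | 0.325 | 0.232 | 0.219 | 27.8% vs 21.9% | 20% |

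*Change of at least 3 at Week 52/ET.* Normal slopes, error SD 1.0: 53.6% vs 53.9%, false benefit 1.7%. Skewed slopes: 9.3% at error SD 0.5, and 38% at 1.0 (39.8% vs 30.7%).

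**Sensitivity, skewed slopes with error SD 1.0 unless stated**
- Switching at Week 12 from 15% to 75%: RRP 6.5% to 36%; change of at least 3, 17% to 56%. The upper end follows from the planned 25% placebo ACR20 rate: a responder improves by 20% in both joint counts and is not switched.
- Early termination of 10% near Week 12 in every arm: RRP 17%. With 151 per arm: RRP 18%.
- Half-point / whole-point scores: RRP 9.8% / 3.4%; change of at least 3, 16% / 40%.
- Reversals: normal slopes with whole-point scores give RRP of 41.0% vs 45.7%, against ASP015K. Change of at most 0 at Week 52/ET gives 30.6% vs 23.7%, a 26% chance of a false result favouring placebo.
- Week 28/ET: a Week 12 switcher needs 3 × 84/196 = 1.29 points to reach 3. The false-benefit chance for that cut is 12% (2.6% with normal slopes).

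**The case against.** The size rests on quantities the documents do not give: reading-error SD, switch rate and scoring step (the last is in a third-party SOP). With skewed slopes, lowering the error SD from 1.0 to 0.5 takes the RRP figure from 20% to 3.6%, and with normal slopes it is nominal throughout. That stands, and it is why no single size can be quoted.

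Much larger figures can be generated. With no true progression, error SD 1 and 40% switching, the Fisher test rejects 88% of the time, and an error SD of 2 or 3 takes this above 99%. A reader might infer that a false positive is close to certain. The documents do not support that. SAP 4 plans a placebo change of 2.0, and inclusion criterion 10 selects patients at risk of joint destruction. The total SDs quoted for comparator active arms, error included, are as low as 1.09, 1.54, 1.83 and 2.01.

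It can also be said that the Week 28/ET category tests share the mechanism. They do: with no progression and error SD 0.5, change of at most 0.5 at Week 28/ET shows a 47% chance of false benefit, against under 0.1% for RRP. The case for keeping them is that only Week 12 switchers and early terminators are extrapolated, the distortion is generally smaller, and the values are those of the primary analysis. They are not free of the problem.

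Finally, for at most 0.5 and at most 0, the extrapolation argument holds only if Week 52/ET is meant. Under EOT, placebo values can be post-switch, which is a different obstacle to comparison with placebo.

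**Conclusion.** The unequal intervals and the Fisher test in row 10.4 are plain in the SAP, as is the same asymmetry for change of at least 3 at Week 52/ET. With reading error these rates can differ without a drug effect, usually to placebo's disadvantage on RRP when most true rates are below 5 per year. Under the stated assumptions the chance of a false RRP benefit runs from about nominal to 20% at 50% switching. It is usually smaller with rounded scores. The assumptions are common slopes, slope independent of switching, full active follow-up and near-continuous scores.

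A reader might also infer that the bias always favours ASP015K, that the pre-switch rule is wrong, or that the primary result is at risk. None follows. The direction reverses in some cases above. The pre-switch rule keeps active-drug time out of placebo slopes. Steps 1 to 4 use neither RRP nor Week 52 values. Mean yearly progression is not biased by this mechanism, and row 12.4.1 only describes it. RRP and the cut at 3 are SAP additions to the protocol's list, and all these tests are unadjusted secondary analyses. Priority: minor to moderate.

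**What to change.** 1. Remove the Fisher test from row 10.4. Report RRP descriptively, with days from baseline film to final film by arm.
2. Report the Week 52/ET comparison with placebo for change of at least 3 descriptively, with the number extrapolated and the source film by arm.
3. Reconcile EOT (rows 10.1 and 10.2; SAP 7.11.4) with Week 52/ET (SAP 7.4.2 and 7.11.1) for at most 0.5 and at most 0. Report those late comparisons descriptively too: placebo values are extrapolated under one reading and can be post-switch under the other.
4. Keep the Week 28/ET category tests, show the number extrapolated by arm, and state that Week 12 switchers carry the same, generally smaller, distortion.
5. Keep the pre-switch rule. Cutting only the ASP015K arms back to Week 28 would not repair RRP, because Week 12 switchers would still be annualised over about 84 days.

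The cost is SAP wording and up to eight unadjusted secondary p-values: RRP for two doses, plus three late categories for two doses (2 + 6). The cut at 0.5 is a protocol secondary variable, but it keeps its Week 28/ET test.

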### 6.1.2.3 Time to Event Variables

- Time to the first ACR20-CRP response up to Week 12
- Time to the first ACR50-CRP response up to Week 12
- Time to the first ACR70-CRP response up to Week 12
- Time to the first occurrence of DAS28-CRP <2.6 up to Week 12
- Time to the first occurrence of SDAI score <= 3.3 up to Week 12
- Time to the first occurrence of CDAI score <= 2.8 up to Week 12
- Time to the first occurrence of ACR/EULAR score for remission up to Week 12

## 6.2 Safety Variables

- AEs
- Vital signs (body temperature, pulse rate and blood pressure in sitting position)
- Body weight
- Central ECG
- 12-lead ECG
- Central electrocardiogram
- Chest radiography
- Laboratory assessments

**Treatment emergent adverse events** (TEAEs) will be defined as any adverse event that started or worsened in severity after initial dose of study drug through Week52 or Withdrawal.

AE for the subjects who switched ASP015K 100 mg or ASP150 mg from Placebo at Week 12 or Week 28 will be handled as follows.

- AE onset before the first dose of week12 study drug will be considered to be occurred at Placebo.
- AE onset after the first dose of week12 study drug before the first dose of week28 study drug will be considered to be occurred at Placebo if the subject did not switch Placebo at Week 12. Else, if the subject switched ASP015K 100 mg or 150 mg at Week12, then the AE onset after the first dose of week12 study drug before the first dose of week28 study drug will be considered to be occurred at ASP015K 100 mg or 150 mg.
- AE onset after the first dose of week28 study drug will be considered to be occurred at ASP015K 100 mg or 150 mg, which is switched treatment from Placebo.

A drug-related TEAE is defined as any TEAE with possible, probable or missing relationship to study drug as assessed by the investigator. Moreover, any TEAE with missing relationship to study drug or reference drug was counted as drug related (probable).

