5.4.3 Adverse Events

The survey period for AEs will be from the initiation of study treatment to before the initiation of administration in the extension study or until the end of follow-up.

Events that occurred after study drug administration until before the initiation of administration in the extension study or until the end of follow-up will be recorded as AEs. Concurrent diseases that worsened during the study will also be recorded as AEs. AEs that occurred after the subject has completed the study plan or has been discharged from the hospital or the study center will not be recorded.

AEs that have not resolved before the initiation of administration in the extension study or at the end of follow-up must be followed-up until resolved or judged to be no longer clinically significant or until they become chronic to the extent that they can be fully characterized. If the event resolves during the study period, the date of resolution is to be entered in the eCRF.

- CONFIDENTIAL -

See Appendix 4 “Liver Safety Monitoring and Assessment” for the assessment of AEs caused by DILI.

Herpes zoster should be entered as an AE information in the eCRF, and also, a separate Herpes Zoster (shingles) Worksheet should be prepared, and a copy should be submitted to the sponsor. If the sponsor considers necessary and requests for submission of forms for the purpose of providing additional information on other AEs, a form must be prepared to report to the sponsor.

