### 7.5.1 Adverse Events

If an AE occurs on the same date as the initial dose date, the subject will be asked to select one of the following (see the eCRF page for AE): onset before initial dose of study drug,

onset after initial dose of study drug. Any AEs occurring after initial dose of study drug through the follow-up period will be considered treatment emergent.

Adverse events will be coded using the Medical Dictionary for Regulatory Activities (MedDRA).

All adverse events reported during the study period will be presented in subject listings.

Only TEAEs in the study period will be analyzed, and 2 types of analyses will be performed: TEAE occurrence analysis and TEAE per 100 patient-years analysis, as described below. TEAE occurrence analysis will be displayed by whole treatment period and by the following period. Primarily, TEAE occurrence analysis for Week 0 to Week 12 will be conducted in the view of comparison with placebo.

TEAE occurrence analysis for overall treatment period will be conducted in focus for ASP015K dose groups.

1. Week 0 to Week 12
2. Week 12 to Week 28
3. Week 28 to Week 52 or Later

TEAE per 100 patient-years analysis will be displayed above category, and by Week 0 to Week 12, and overall period.

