#### Definition 1:

TEAEs per 100 PYs =  $100 \times (\text{Number of subjects who had at least 1 incidence} / \text{Total PYs})$

Total PYs will be calculated by summing individual subjects' durations.

If subjects had at least 1 predefined AE, then the duration of these subjects are summed as from initial dose up to first incidence of predefined AEs.

If subjects had no predefined AE, then the duration of these subjects are summed as from initial dose through follow-up. Summed duration will be divided by 365.25 to represent per year.

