#### Definition 2:

TEAEs per 100 PYs =  $100 \times (\text{Number of TEAEs for all subjects in the treatment group} / \text{Total PYs in the treatment group})$ .

For number of TEAEs for all subjects in the treatment group, multiple occurrences of the same TEAE in the same subject will be counted multiple times.

Total PYs will be calculated by summing subjects' durations in study through the follow-up period. Each subject's duration will be calculated as:  $(\text{last date of follow-up in the study} - \text{date of initial dose of study drug} + 1) / 365.25$ .

Patient-Year analysis will be calculated by Placebo, 100 mg, 150 mg, 100mg+150mg, ASP015K Total, Total.

The number of TEAEs and AEs per 100 PYs will be provided by Definition 2, for all TEAEs (if analyzable), by SOC and PT for each treatment group, ASP015K Total and Total.

Patient-Year analysis for following specified AE will also be conducted by Definition 1 with 95% confidence interval.

- Serious Infections
- Malignancies
- Herpes Zoster Related Disease (Herpes Zoster and Varicella)
- Herpes Zoster
- Varicella
- Infections That Require Intravenous Anti-infectious Therapy

Note: Definition will be provided in the Appendix 8.

Confidence Interval for TEAEs per 100 patient-years will be calculated for AE of special Interest based on following formula (assuming Poisson distribution).

- Upper limit of CI (TEAEs per 100 PYs) :  $100 * \exp\left(\log\left(\frac{A}{T}\right) + Z_{\alpha} * \sqrt{\frac{1}{A}}\right)$
- Lower limit of CI (TEAEs per 100 PYs) :  $100 * \exp\left(\log\left(\frac{A}{T}\right) - Z_{\alpha} * \sqrt{\frac{1}{A}}\right)$

A: Number of subjects who had at least 1 incidence

T: Total PYs by 100 PYs as one unit

$Z_{(\alpha)}$ : alpha % point of standard normal distribution

alpha = 0.025

In addition, the subgroup analysis of Sex, Age Group, Concomitant Steroid at Baseline, and Predonisone Dose at Baseline will be conducted.

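### SAP 6.2 ends the TEAE window at Week 52 or withdrawal, but 7.5.1 and the patient-year denominators in 7.5.1.2 run through follow-up; if 6.2 is programmed, overall-period rates are biased low by about 1% to 8% per arm

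*SAP*

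**What the plan says.** The SAP defines the TEAE twice.

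- **SAP 6.2 (Safety Variables):** "any adverse event that started or worsened in severity after initial dose of study drug through Week52 or Withdrawal".
- **SAP 7.5.1 (Adverse Events):** "Any AEs occurring after initial dose of study drug through the follow-up period will be considered treatment emergent".

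The same section 7.5.1 adds "Only TEAEs in the study period will be analyzed", so the TEAE definition decides which events reach the incidence tables and the patient-year analysis.

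The person-time in SAP 7.5.1.2 uses the longer window under both definitions.

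- **Definition 1** (subjects with at least one event, used for adverse events of special interest): "If subjects had no predefined AE, then the duration of these subjects are summed as from initial dose through follow-up".
- **Definition 2** (numerator "Number of TEAEs for all subjects in the treatment group"): "Total PYs will be calculated by summing subjects' durations in study through the follow-up period".

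In the SAP key terms, treatment ends with the Week 52 or withdrawal visit, and follow-up is a separate period of up to 4 weeks after it. For subjects who enter the extension, follow-up ends when extension treatment starts. Footnote 2 of the schedule of assessments says that no follow-up is done when the extension starts immediately after Week 52.

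On data collection, protocol 5.4.3 states: "The survey period for AEs will be from the initiation of study treatment to before the initiation of administration in the extension study". The sentence then gives the end of follow-up as the alternative endpoint, so events in follow-up are collected.

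**The concern.** The two definitions give different event sets from the same data. The difference is every event that starts or worsens between the Week 52 or withdrawal visit and the end of follow-up. The SAP has a single version (1.00), so both sentences are current, and two programmers who each follow the document could produce different TEAE tables.

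Two things are at stake if the 6.2 sentence is the one programmed.

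- **Incidence tables.** A serious infection or herpes zoster with onset in follow-up would not be tabulated as a TEAE. It would appear only in the subject listings, which cover all events in the study period.
- **Patient-year rates.** The numerator stops at Week 52 or withdrawal while the denominator continues through follow-up. Person-time then accrues during which no event can count. Under Definition 1, a subject whose first event falls in follow-up would be treated as event-free and would also add the follow-up time.

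Section 7.5.1.2 gives its purpose as adjusting for unequal time in study and for differential dropout. The mismatch works against that purpose, because the amount of follow-up time depends on withdrawal and extension uptake and so may differ between the 100 mg and 150 mg arms.

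**Working it through.** The plan gives no expected TEAE rate, event count or total patient-years, so there is no figure of its own to reproduce. The check compares the windows and then sizes the mismatch.

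**Step 1. The windows side by side**

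| Place | End of window |
|---|---|
| SAP 6.2, event counted as a TEAE | Week 52 or withdrawal |
| SAP 7.5.1, event counted as a TEAE | End of follow-up |
| SAP 7.5.1.2, Definition 1 person-time, event-free subjects | End of follow-up |
| SAP 7.5.1.2, Definition 2 person-time, all subjects | End of follow-up |
| Protocol 5.4.3, adverse event collection | End of follow-up or start of extension dosing |

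Only 6.2 stops early. With the 7.5.1 numerator, numerator and denominator cover the same time and the mismatch factor is 1.

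**Step 2. One subject, 6.2 numerator with 7.5.1.2 denominator**

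Inputs: Week 52 is Day 365 in the schedule of assessments, and follow-up is 28 days in the key terms. Assume a constant event rate over treatment and follow-up. For Definition 2 with D days to Week 52 or withdrawal:

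estimated rate / true rate = D / (D + 28)

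- Completer with full follow-up: 365/393 = 0.929, or 7.1% low. In whole weeks the follow-up share is 28/(364 + 28) = 28/392 = 7.1%.
- Withdrawal at Day 197 (Week 28): 197/225 = 0.876, or 12.4% low.
- Withdrawal at Day 85 (Week 12): 85/113 = 0.752, or 24.8% low.
- Completer who enters the extension immediately: no follow-up time, so no bias.

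**Step 3. A whole arm, Definition 2**

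Reported rates pool subjects, so the relevant factor is (mean D) / (mean D + mean follow-up days). Let w be the proportion withdrawing and f the proportion of completers with a full 28-day follow-up. Assume a mean withdrawal day of 183 and 28 days of follow-up for every withdrawn subject. These values are assumptions; the documents do not give them.

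- mean D = 183w + 365(1 − w)
- mean follow-up = 28w + 28f(1 − w)

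For w = 0.10, mean D = 18.3 + 328.5 = 346.8 days:

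| f | Mean follow-up (days) | Ratio | Bias |
|---|---|---|---|
| 0 | 2.8 | 346.8/349.6 | −0.8% |
| 0.25 | 9.1 | 346.8/355.9 | −2.6% |
| 0.50 | 15.4 | 346.8/362.2 | −4.3% |
| 1 | 28.0 | 346.8/374.8 | −7.5% |

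For w = 0.30, mean D = 54.9 + 255.5 = 310.4 days, and the bias runs from −2.6% (f = 0: 310.4/318.8) to −8.3% (f = 1: 310.4/338.4).

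**Step 4. A whole arm, Definition 1**

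Assume an exponential time to first event with rate λ, all subjects treated to T = 365 days and all followed for 28 days more. With the 6.2 numerator:

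estimated rate / λ = (1 − e^(−λT)) / [(1 − e^(−λT)) + 28λ·e^(−λT)]

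| True rate per 100 PY | Estimate | Bias |
|---|---|---|
| 0.5 | 0.46 | −7.1% |
| 3 | 2.79 | −7.0% |
| 10 | 9.32 | −6.8% |
| 50 | 47.2 | −5.6% |

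This is near the upper end for Definition 1, because every subject is given a full follow-up.

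**The case against.** The best case for the plan is that 7.5.1 is the operative analysis section and everything around it agrees with it. Both person-time definitions end with follow-up, the protocol collects events to the same point, and the label of the last reporting period in 7.5.1 allows for time after Week 52. On that reading 6.2 is a stray sentence and no rate is biased. This stands in part. It makes the 7.5.1 window the natural one to keep, and it means that the bias is conditional. It does not remove the contradiction: 6.2 is the section that formally defines the variable, no text ranks the two, and the matching columns in Tables 16 and 17 of Appendix 3 stop at Week 52.

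Three stronger readings are tempting, and the documents do not support them.

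- **That the patient-year rates are diluted as planned.** They are diluted only if the numerator follows 6.2.
- **That the bias may reach 25%.** The share 28/(84 + 28) = 25% describes one subject who withdraws at Week 12. Rates are reported by treatment group, where the scenarios above give about 1% to 8%.
- **That the loss is greatest in patients who stop because of an adverse event.** The arithmetic depends on when a subject stops, not why. The event that leads to stopping normally begins before withdrawal and counts under either definition. What can be lost is a later new or worsening event.

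The reach is also limited. In the patient-year table of Appendix 3, the overall-period analysis covers 100 mg and 150 mg only, so it contains no placebo contrast to distort. Section 7.5.1 makes Week 0 to 12 the main comparison with placebo for TEAE occurrence. There the choice of definition matters only for events after a withdrawal before Week 12. Follow-up events also stay visible in the listings.

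**Conclusion.** The point holds in conditional form. SAP 6.2 and 7.5.1 give incompatible TEAE windows in current text, and the plan does not say which one applies. Following 6.2 as written, together with 7.5.1.2 as written, leaves follow-up events out of the TEAE tables and biases the overall-period patient-year rates for 100 mg and 150 mg downward.

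The size is modest: 7% for a completer with full follow-up, zero for a subject who goes straight into the extension, and about 1% to 8% for an arm. The arm-level range rests on a constant event rate, 10% to 30% withdrawal at a mean of Day 183, 28 days of follow-up for each withdrawn subject, and between none and all of the completers having a full follow-up. None of these is a document figure. If 7.5.1 is programmed, the bias from this source is zero.

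This is an inconsistency that should be corrected because it affects the central safety variable and is cheap to remove. It does not show that the planned safety rates are wrong.

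**What to change.** Change the one sentence in SAP 6.2 so that a TEAE is an event that starts or worsens in severity from the first dose to the end of the follow-up period as defined in the SAP key terms. For subjects who enter the extension, that period ends at the first extension dose. Sections 7.5.1 and 7.5.1.2 already use this window and need no new one, and it agrees with adverse event collection in protocol 5.4.3. The last column label in Tables 16 and 17 of Appendix 3 should be brought into line with the period label in 7.5.1.

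The cost is one sentence and one label, plus a change to the TEAE flag if it has already been programmed from 6.2. No data collection or clinical procedure changes. The SAP is to be final before unblinding. If it can no longer be amended, the clinical study report should state which window was used and why, and confirm that numerator and person-time share it.
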